6.3. Storage

6.3.1. Rilzabrutinib/Placebo

Rilzabrutinib or placebo tablets are supplied in 100cc bottles. The recommended storage condition is 2 to 25°C (IB).

6.4. Drug Management

Drug management will be the responsibility of the Investigator of the medical institution. The Investigator, the pharmacist of the medical institution, or another designated person must complete, in real time, all the documents concerning treatment management. Treatment management will be verified on a regular basis by the study monitor.

The study medication should be used only by healthcare professionals who are qualified by training and experience in the safe use and handling of investigational drugs.

During the COVID-19 pandemic, drug supply can be sent to participants when the participant is not able to travel to the site or the site cannot host a participant visit. Site instructions for shipment of supplies directly to participants and procedures for conducting remote site visits inclusive of ensuring drug supply maintenance are described in “Guidelines to Sites for Delayed Participant Visits or Missed Visits due to travel restrictions and any foreseeable impacts of COVID-19” ([Appendix 8](#)).

6.4.1. Drug Accountability

The Investigator or his/her designated representatives will dispense study medication per the SoA ([Table 1](#), [Table 2](#), and [Table 3](#)).

The Investigator is responsible for the control of drugs under investigation. Adequate records of the receipt (eg, Drug Receipt Record) and disposition (eg, Investigational Drug Dispensing Log) of the study medication must be maintained. The Investigational Drug Dispensing Log must be kept current and should contain the following information:

- The identification (ID) of the participant to whom the study medication was dispensed (that is, participant ID number, and year of birth)
- The date(s), quantity, and lot number(s) of the study medication dispensed to the participant
- The ID of the person who dispensed the study medication

All used and unused drug supplies must be returned by the participant at every visit.

All records and used and unused drug supplies must be available for inspection by the study monitor at every monitoring visit. Reconciliation of all drug supplies (rilzabrutinib or placebo) will be performed by the study monitor.

6.4.2. Destruction of Investigational Medicinal Product

When the study is completed, any used and unused study medication (eg, empty, partially used, and unused containers) will be destroyed on-site or returned to the depot of destruction as requested. Copies of the completed Drug Dispensing Log and Drug Return Record(s) will be returned to the Sponsor. The Investigator's copy of the Drug Return Record(s) must accurately document the return of all drug supplies to the Sponsor.

Local or institutional regulations may require immediate destruction of used investigational medicinal product (IMP) for safety reasons. In these cases, it may be acceptable for investigational study center staff to destroy dispensed IMP before a monitoring inspection, provided that source document verification is performed on the remaining inventory and reconciled against the documentation of quantity shipped, dispensed, returned, and destroyed, and provided that adequate storage and integrity of drug has been confirmed. Written authorization must be obtained from the Sponsor or Sponsor designee after final accountability prior to destruction.

Unused study medication from the site that has not been stored properly should not be destroyed until the monitor and/or Sponsor approve the destruction.

No destruction of unused (not dispensed) IMP takes place without Sponsor's written authorization. Storage conditions must be kept until approval from the Sponsor to remove the product from its storage location (eg, refrigerator). Products must be kept in a dedicated quarantine area until destruction, with a clear sign of "quarantined" until the Sponsor's Site Monitor authorizes the destruction.

Written documentation of destruction must contain the following:

- Identity of IMP(s) destroyed
- Quantity of IMP(s) destroyed
- Date of destruction
- Method of destruction
- Name and signature of responsible person who destroyed the IMP

If a site does not have a destruction SOP, study drug can be returned to the depot.

6.4.3. Treatment Compliance

Accountability and participant compliance will be assessed by maintaining adequate study medication dispensing records and medication counts. The Investigator is responsible for ensuring that dosing is administered in compliance with the protocol. See Section 6.4.1 for instructions on Drug Accountability procedures.

6.4.4. Treatment Blinding/Unblinding

Allocation of participants to treatment groups will proceed through the use of an interactive web response system (IRT/IWRS) that is accessible 24 hours a day, 365 days a year.

- The randomized intervention kit number list is generated centrally by the IRT/IWRS.
- The randomization and intervention allocation are performed centrally by the IRT/IWRS. The IRT/IWRS generates the participant randomization list and allocates the intervention number and the corresponding intervention kits to the participants according to it.
- A randomized participant is a participant from the screened population who has been allocated to a randomized intervention by the IRT/IWRS regardless of whether the intervention was received or not.

The pharmacist or designee will be required to enter or select information that will include, but not be limited to; the user ID, and password, participant number, participant year of birth, as well as other information (as allowed locally). The pharmacist or designee will then be provided with a participant randomization number and treatment assignment. Once participant numbers and randomization numbers have been assigned, they cannot be reassigned. The randomization system will also send confirmation of the randomization, by email or fax, to the user. Specific instructions will be provided in the IWRS study reference guide. Access to the randomization code will be limited; all Sponsor personnel (and representatives), and site personnel who are directly involved in the conduct of the study will be blinded to randomization codes.

The treatment each participant receives will not be disclosed to the Investigator, study center personnel, participants, or the Sponsor or representatives on the clinical study team. Further details for blinding and dispensing of blinded treatment are provided in the Pharmacy Manual.

If deemed by the Investigator to be medically necessary, the Investigator can unblind a participant via the IWRS after consultation with Sponsor medical monitor (See [Appendix 10](#) for UK country-specific requirements).

Sponsor PV operations/responsible third party may unblind the intervention assignment for any participant with a suspected unexpected serious adverse reaction (SUSAR). If the SUSAR requires that an expedited regulatory report be sent to one or more regulatory agencies, a copy of the report, identifying the participant's intervention assignment, may be sent to Investigators in accordance with local regulations and/or Sponsor policy.

At the facilities where the systemic drug concentration measurements and selected biomarkers are determined, the samples will be analyzed prior to data base lock leading to unblinding of responsible bioanalysts. Bioanalysts are excluded from the clinical trial team. One programmer may be unblinded to prepare the dataset for population PK analysis, and there will be strict procedures to maintain blind beyond the programmer.

6.5. Treatment of Overdose

An overdose (accidental or intentional) with the IMP is an event suspected by the Investigator or spontaneously notified by the participant and defined as a single ingestion of a dose equal to or greater than 1200 mg (≥ 3 times the indicated single dose of 400 mg) provided that it has been taken at once or over a 2-hour period. No specific information is available on the treatment of overdose of rilzabrutinib.

In the event of an overdose, the Investigator/treating physician should:

1. Evaluate the participant to determine, if possible, whether study intervention should be interrupted or whether the dose should be reduced.
2. Closely monitor the participant for any AE/SAE and laboratory abnormalities until rilzabrutinib can no longer be detected systemically (at least 20 hours).
3. Obtain a plasma sample for PK analysis within 20 hours from the date of the last dose of study intervention if possible.
4. Document appropriately in the eCRF

6.6. Concomitant Medications

6.6.1. Prohibited Medications

The following medications are prohibited for use during the study:

- Concomitant use of any ***immunosuppressant medication***, other than CS, as described in this protocol. Participants who need other immunosuppressant therapy during the study must be withdrawn. See Exclusion # 7, Section [5.2](#) for washout periods
- Concomitant use of known ***strong-to-moderate inducers or inhibitors of cytochrome P450 (CYP) 3A***. See Exclusion # 10, Section [5.2](#) for washout periods

- **Proton pump inhibitors** are not permitted. Esomeprazole was shown to reduce the exposure of rilzabrutinib by approximately 50%, presumably due to the effects of a lack of an acidic environment on tablet dissolution. Participants who are on proton pump inhibitors should be changed to H2 receptor blocking drugs if possible or not enroll in the study. Details of H2 receptor blocker administration is provided in Section 6.6.2. See Exclusion # 9, Section 5.2.
- **Rescue medications** other than one of IVIg, high-dose CSs, platelet infusion, or anti-D immunoglobulin infusion intended to increase platelet counts or prevent bleeding when platelet counts are less than $20 \times 10^9/L$, or for bleeding or wet purpura, are not permitted
- **COVID-19 vaccine** is prohibited during the last 12 weeks of the blinded treatment period.
- **Live vaccines** are not permitted during the study.

6.6.2. Particular Permissible Medications

The following medications are permitted for use during the study:

- ITP medications, an oral CS and/or a TPO-RA (authorized for the treatment of ITP)

Note:

- These medications must be maintained at stable doses from 14 days before Study Day 1 and until the last dose of study medication. Adjustments in the doses of concomitant ITP medications will be permitted for associated safety concerns only.
- Administration of corticosteroids and TPO-RAs should follow corresponding updated package inserts/SmPCs of the marketing authorization.
- Tapering is allowed during LTE period only due to achieving durable platelet response, and would follow the following guidelines with 2 weekly platelet counts between tapers:
 - 10 mg/day every one to two weeks from an initial dose >40 mg of prednisone or equivalent per day
 - 5 mg/day every one to two weeks at prednisone doses ≤ 40 to >20 mg or equivalent per day
 - 2.5 mg/day every one to two weeks at prednisone doses ≤ 20 to >10 mg or equivalent per day
 - 1 mg/day every one to two weeks at prednisone doses ≤ 10 to >5 mg or equivalent per day
 - 0.5 mg/day every one to two weeks at prednisone doses ≤ 5 mg or equivalent per day down to zero. This can be achieved by alternating daily doses (eg, 5 mg on day one and 4 mg on day two)
 - Dose of corticosteroid can be up titrated if platelet counts fall below $50,000/\mu L$ on two consecutive measurements
- IVIg or high- dose CS, platelet infusion, or anti-D immunoglobulin infusion as rescue medications

- Clinically relevant drugs that are substrates of CYP3A, including those considered to be sensitive CYP3A substrates. Appropriate caution should be used when co-administering sensitive CYP3A substrates with rilzabrutinib, including an assessment of medical risk-benefit for each medication. Consideration should also be given to avoidance of high doses, dose reduction, or replacement of sensitive CYP3A substrate drugs
- H₂ receptor blocking drugs (ranitidine or famotidine) and antacids are permitted provided they can be given 2 hours or more after administration of rilzabrutinib or placebo

7. STUDY ASSESSMENTS AND PROCEDURES

7.1. Study Recruitment Procedures

Participants will be identified for potential recruitment by the Investigator using a recruitment plan agreed upon with the Sponsor, possibly including, but not limited to, a listing from a study center, volunteer database, newspaper/radio/internet advertisement, or mailing list.

7.2. Study Enrollment Procedures

Participants eligible for screening cannot commence enrollment study procedures until the informed consent process and form has been properly administered and signed. Screening tests are then administered, including blood tests sent for laboratory testing. Where the clinical significance of an abnormal screening test result (lab or any other tests) is considered uncertain, the test may be repeated once at least 7 days apart.

The Investigator or designee will enter data for each enrolled participant in the study electronic case report form (eCRF) and enter the corresponding participant ID number in the appropriate place on each participant's eCRF. A participant enrollment and Identification Code List must be maintained by the investigator or pharmacist, or designee.

Under no circumstances will participants who enroll in this study and complete treatment as specified be permitted to re-enroll in the study.

During the COVID-19 pandemic, the Sponsor will need to assess the feasibility of implementing a plan for participant access to study drug and any additional measures required to monitor participant safety on an ongoing basis. Please notify the Sponsor and your contract research organization (CRO) study monitor if your site suspends participant enrollment.

7.3. Temporary Discontinuation

Temporary intervention discontinuation may be considered by the Investigator because of suspected AEs or disruption of the clinical trial due to a regional or national emergency declared by a governmental agency. For all temporary intervention discontinuations, duration should be recorded by the Investigator in the appropriate pages of the CRF or eCRF. The Investigator should make the best effort to resume the IMP as early as clinically and practically possible. All efforts should be made to follow the study procedures as per the SoAs during temporary disruption of study medication.

Temporary discontinuation decided by the Investigator corresponds to a period of >2 missed consecutive doses of IMP.

7.4. Rechallenge

Reinitiation of the IMP will be done under close and appropriate clinical and/or laboratory monitoring once the Investigator will have considered according to his/her best medical IMP judgment that the benefit/risk balance is in favor of resuming the IMP and if the selection criteria for the study are still met.

7.5. Participant Exit from the Study

7.5.1. Individual Participant Stopping Rules

- Life-threatening or Common Terminology Criteria for Adverse Events (CTCAE) Grade 4 rilzabrutinib-related TEAE except for AEs related to the disease under study or other underlying medical conditions
- Serious allergic reaction to rilzabrutinib or placebo including anaphylactic reaction
- Pregnancy
- Any medical condition or personal circumstance that, in the opinion of the Investigator, exposes the participant to risk if the participant continues with rilzabrutinib or placebo or that prevents the participant's adherence to the protocol
- Human immunodeficiency virus/acquired immune deficiency syndrome (AIDS), viral hepatitis (B and C) infection occurring during the study
- Violation of protocol inclusion or exclusion criteria, that in the opinion of the Sponsor, would significantly compromise data interpretation
- Discontinuation of study intervention for abnormal liver tests is required by the Investigator when a participant meets one of the conditions outlined in [Appendix 15](#) or in the presence of abnormal liver chemistries not meeting protocol-specified stopping rules if the Investigator believes that it is in best interest of the participant.

No follow-up or additional procedures will be performed on participants who discontinue before receiving rilzabrutinib or placebo. For participants who discontinue after receiving any amount of rilzabrutinib or placebo, the reason for a participant's discontinuation from the study must be clearly documented in the participant's medical records and on the appropriate page of the eCRF, and participants will be asked to complete the ET assessments (see [Table 1](#), [Table 2](#) and [Table 3](#)).

7.5.1.1. Individual Long-term Extension Participant Stopping Rules

Participants may be withdrawn from the study if the participant is no longer responding according to the table below:

Time in the Long-Term Extension (LTE)	"No response" platelet counts defined as <30,000/μL or <20,000/μL above baseline based on:
During the first 12 months in the LTE	2 consecutive monthly visits
After the first 12 months in the LTE	1 quarterly visit In this case a second platelet count has to be obtained in one month to confirm lack of response. If the platelet count met the no response criteria, the participant may be terminated.

7.5.2. Participant Withdrawal

All participants have the right to withdrawal of consent and discontinue participation without prejudice at any time during the study. Every effort should be made to comply with the protocol; however, participants will be withdrawn from the study entirely with no further study visits if any of the following situation arise:

- Withdrawal of participant's consent or participant's request to discontinue from the study for any reason
- The participant is unwilling or unable to comply with the protocol

Participants who are withdrawn from the study will not be replaced. The reason for the participant's withdrawal from the study should be recorded on the eCRF.

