- u* This visit is for platelet count assessment and can be conducted on-site or remotely. After the end of treatment (EOT) visit, weekly platelet count assessment is not required; however, it is up to the Investigator to decide whether to conduct weekly platelet assessments using unscheduled visits, if deemed necessary for participant safety.
- v* SARS-CoV-2 molecular test (if COVID-19 testing is required per local guidelines to be determined for each site).
- w* During the blinded treatment period (Week 13 to Week 24): Participants who discontinue from the blinded treatment period due to safety (or other) reasons and choose to join the open label period will attend the Week 25 assessments at their next scheduled visit.
- x* **All participants who discontinue treatment during the blinded or open-label period need to have an Early Termination visit as specified in Table 1 and an End of Study visit (4 weeks after last IMP intake) as specified in the End of Study visit in Table 2 (See End of Study [Table 2](#)).**

Table 2 - Schedule of Assessments - Open Label Period

	Open Label Period								End of Study 4 weeks post-last dose SD393	Weekly Lab Visits Between Clinic Visits ^r	Early Termination/ Unscheduled visit
	First Day of WK25 ^{a, p} SD169	WK 29 SD197	WK33 SD225	WK37 SD253	WK41 SD281	WK45 SD309	WK49 SD337	First Day of WK53 ^q SD365			
Visit Window	±3 days	±3 days	±3 days	±3 days	±3 days	±3 days	±3 days	±3 days	±3 days	±3 days	
AEs	X	X	X	X	X	X	X	X	X		X
Concomitant Medications	X	X	X	X	X	X	X	X	X		X
Height (cm) ^a	X			X				X			
Weight (kg)	X	X	X	X	X	X	X	X	X		X
Physical exam ^b	X	X	X	X	X	X	X	X	X		X
ECG (12-lead, single)	X ^c							X	X		X
Vital Signs	X	X	X	X	X	X	X	X	X		X
Urinalysis ^d	X	X	X	X	X	X	X	X	X		X
Pregnancy test ^e	X	X	X	X	X	X	X	X	X		X
Serum Chemistry ^f	X	X	X	X	X	X	X	X	X		X
Hematology, differential, reticulocytes ^g	X	X	X	X	X	X	X	X	X	X ^r	X
T/B/NK counts ^m	X	X	X		X			X	X		
PT/INR, aPTT ^h	X	X	X	X	X	X	X	X	X		
TPO levels ^m	X	X	X	X	X	X	X	X	X		
Hemolysis panel ^{i, m}	X	X	X	X	X	X	X	X	X		
Immunoglobulin Levels ^m	X	X	X		X			X	X		
PK sample ⁱ	X							X			X
BTK Occupancy (at select sites) ^{k, m}	X							X			
(Optional) sample for vaccine-specific IgG ^{m, n}	←=====→										X
QOL Questionnaires ^l	X	X	X	X	X	X	X	X	X		X
IBLS	X	X	X	X	X	X	X	X	X		X
Rilzabrutinib dispensed	X	X	X	X	X	X	X	X			
Patient Medication Diary	X	X	X	X	X	X	X	X			
SARS-CoV-2 test (see Appendix 10 for country-specific requirements)	X										

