During the blinded treatment period (Week 13 to Week 24):

- Participants who discontinue from the blinded treatment period due to safety or other reasons and choose to join the open label period will undergo the Week 25 assessments at their next scheduled visit.

[figure not shown]
Participants who discontinue the blinded treatment period and choose not to join the open label period, should attend an Early Termination (ET) visit as shown in the Schedule of Assessments (SoA) (Table 1) for collection of data at the time of study discontinuation and complete the follow-up (EOS visit) and any further evaluations in need of completion.

Concomitant ITP medications (an oral CS and/or a TPO-RA) will be permitted in both treatment arms and must be maintained at stable doses from 14 days before Study Day 1 and until the last dose of study medication. Reductions in the doses of concomitant ITP medications will be permitted for associated safety concerns only. In the LTE portion of the trial, reductions in dose or withdrawal of concomitant ITP medications (an oral CS and/or a TPO-RA) will also be permitted if the participant achieves platelet count of $\geq 50,000/\mu\text{L}$ in three scheduled visits (over 12 weeks). Retreatment with the same medication(s) and doses of ITP concomitant medication(s) used at baseline (an oral CS and/or a TPO-RA), changing the dose or initiation of new ITP

medications (an oral CS and/or a TPO-RA) will also be allowed. Tapering of concomitant CS should be performed in accordance with the schedule in Section 6.6.2.

The use of rescue medications (one of IVIg, high-dose CSs, platelet infusion, or anti-D immunoglobulin infusion) intended to increase platelet counts or prevent bleeding when platelet counts are less than 20,000/ μ L, or for bleeding or wet purpura, will be allowed.

Figure 2 - Study Design Flow Chart

* Week 25 visit is the last visit of the blinded treatment period and also serve as the start of the open-label period.

Note: Responders will join start open-label period at Week 25.

Non-responders in blinded treatment period can join open-label period directly after Week 12.

BID = twice daily; CS = corticosteroid; PLT = platelet; SOC = standard of care; TPO-RA = thrombopoietin receptor agonist.

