4.1.4. End of Study visit (Four Weeks Post Last Dose of Study Drug)

The following assessments will be performed four weeks post last dose of study drug in the double blind, open label period, or LTE:

- Complete ITP-PAQ or ITP-KIT, EQ-5D-5L and PGIS-Fatigue/PGIS/PGIC patient questionnaire
- Record concomitant medications
- Record AEs

- Record weight (kg)
- Conduct full physical examination; See [Appendix 10.6](#) for Italy-specific requirements
- Complete IBLS
- Capture vital signs (body temperature, respiratory rate, blood pressure, and pulse rate)
- Collect 12-lead single ECG
- Collect urine sample for urinalysis
- Conduct urine pregnancy test (women of childbearing potential)
- Collect clinical laboratory blood samples:
 - Hematology (hemoglobin, hematocrit, RBCs, platelets, mean platelet volume, WBCs with differentials [neutrophils, eosinophils, basophils, lymphocytes, and monocytes])
 - Serum chemistry (AST, ALT, bilirubin, ALP, albumin, creatinine, urea, total protein, sodium, chloride, calcium, phosphate, potassium, and glucose [random])
 - Coagulation (PT/INR, thrombin time, aPTT, fibrinogen level)
- Collect exploratory laboratory blood samples (see [Appendix 10](#) for country-specific requirements):
 - T/B/NK counts
 - TPO levels
 - Hemolysis panel
 - Immunoglobulin levels
 - (Optional) vaccine-specific IgG response
- For country-specific requirements please refer to [Appendix 10](#).

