7.5.3. Participant Lost to Follow-up

At the start of the study, the Investigator should try to obtain all relevant contact details for the participant to facilitate contacting the participant, if necessary. In addition, each participant should be encouraged to attend all study visits for which the participant is scheduled.

If a participant discontinues the study without notifying the Investigator, the Investigator must make every effort to contact the participant to identify the reason for the participant's discontinuation and to encourage the participant to complete the applicable ET visit assessments (see [Table 1](#), [Table 2](#) and [Table 3](#)). If documented attempts to contact the participant fail, and a reason for the participant's discontinuation is undiscoverable, the Investigator can declare the participant as "lost to follow-up" at the end of the study. The Investigator should document in the corresponding medical record all efforts to contact the participant.

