7.8.6. Early Termination Visit

Please refer to [Table 1](#) (if terminating during double-blind treatment) and [Table 2](#) (Open-Label Period) for specific ET assessments. An attempt should be made to have the participant return for the ET visit as soon as possible after the last dose of rilzabrutinib or placebo.

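### Section 7.5.2 rules out all further visits for dosed participants who cannot comply or ask to leave, which conflicts with the exit visits set elsewhere in the protocol

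*Protocol*

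**What the plan says.** Protocol Section 7.5.2 states that "participants will be withdrawn from the study entirely with no further study visits if any of the following situation arise". Two bullets follow. The first pairs withdrawal of consent with a participant's "request to discontinue from the study for any reason". The second covers a participant who will not or cannot comply. The section does not separate dosed from undosed participants, does not mention the ET or End of Study visit, and does not ask whether the participant still agrees to follow-up.

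Other parts of the protocol deal with the same moment:

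- **Section 7.5.1** reserves the absence of follow-up for people who leave before any dose. After any amount of study drug, the reason for leaving the study is recorded and "participants will be asked to complete the ET assessments".
- **Table 1 footnote x** says: "All participants who discontinue treatment during the blinded or open-label period need to have an Early Termination visit as specified in Table 1". It adds an End of Study visit four weeks after the last dose.
- **Section 4** directs those who stop the blinded period and do not join the open-label period to the ET visit and then to the End of Study visit.
- **Section 7.5.3** has the site contact a participant who left without notice and "encourage the participant to complete the applicable ET visit assessments".
- **Section 7.8.6** says: "An attempt should be made to have the participant return for the ET visit as soon as possible after the last dose".
- **Section 4.1.4** sets the content of the last visit: "The following assessments will be performed four weeks post last dose of study drug in the double blind, open label period, or LTE". It does not speak about withdrawn participants, so it shows only that the visit is planned for every period.

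**The concern.** A site handling the exit of a dosed participant finds two incompatible instructions and no rule of precedence. Under one, the participant is asked back for an exit visit and again four weeks after the last dose. Under the other, contact through study visits stops at once.

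Withdrawal of consent properly ends visits, and that part of 7.5.2 is not in question. The difficulty is that the same rule is applied to people who have not necessarily refused follow-up. Someone who cannot keep a weekly blood-count schedule may be willing to attend one or two safety visits.

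At stake are the exit and off-drug safety data of dosed participants: ECG, chemistry, hematology, a pregnancy test where applicable, and adverse events that arise after the last dose. Section 9.3.9.1 adds no safety net for new events, since it places no duty on investigators to look for them once participation has ended.

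**Working it through.** The plan states no figure to reproduce. The check is a comparison of instructions, a count of what a site would lose, and a trace into the SAP.

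**1. Same participant, two instructions (dosed participants).**

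| Situation | Section 7.5.2 | Elsewhere |
|---|---|---|
| Cannot comply | No visits | 7.5.1: a circumstance that stops the participant adhering to the protocol leads to ET assessments |
| Asks to leave the study | No visits | 7.5.1: discontinuation after any dose leads to ET assessments; footnote x: ET and End of Study once treatment stops in the blinded or open-label period |
| Leaves the blinded period, does not join open label | No visits, if for either reason above | Section 4: ET and End of Study |
| Leaves without telling the site | Not addressed | 7.5.3: contact and encourage ET |

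The first row is the clearest conflict: neighbouring sections give opposite orders for what can be the same fact. The last row adds an anomaly. A participant who disappears is pursued for ET assessments, while one who tells the site is offered none.

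**2. Is it only a difference of subject?** Footnote x and Section 4 concern stopping treatment or leaving the blinded period, and 7.5.2 concerns leaving the study. That does not dissolve the conflict. The ET sentence in 7.5.1 is itself about discontinuing the study, and a dosed participant withdrawn under 7.5.2 also stops treatment.

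**3. What a site loses if it follows 7.5.2.** Inputs are the ET column of Table 1 and the End of Study column of Table 2. Each has one ECG, one chemistry panel, one hematology panel and, for women of childbearing potential, one pregnancy test.

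- Scheduled visits: ET + End of Study = 1 + 1 = 2.
- ECGs, chemistry panels, hematology panels, and pregnancy tests where applicable: 1 + 1 = 2 of each.
- Active off-drug adverse event collection: up to 4 weeks × 7 days = 28 days.
- An adult who stops before the Week 25 assessments has, after Day 1, only the ET and End of Study ECGs scheduled. Under 7.5.2, 0 of these 2 remain.

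Table 3 has ET and End of Study columns with the same four tests, so the count also applies in the long-term extension. Footnote x does not reach that period; Sections 7.5.1 (which cites Table 3) and 4.1.4 do.

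**4. Where the lost data would have gone.** SAP Section 3.1 counts events in the post-treatment period as treatment-emergent. SAP Section 3.6.3.1 bases the analysis of potentially clinically significant abnormalities on each participant's worst value in the treatment-emergent period. Removing observations from a worst-value or any-event count can lower the number of participants counted but cannot raise it.

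The by-visit laboratory and ECG summaries use on-treatment data only, so they lose nothing off drug. The confirmatory efficacy analyses (SAP Sections 3.2.2 and 3.3.1.2) treat data after the double-blind on-treatment period as non-response or missing, impute them from on-treatment data, or stop at the last blinded dose. Losing off-drug visits does not affect them.

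**The case against.** The strongest reply is that the protocol's intent is clear. Footnote x is categorical, Appendix 11.14 records it as a clarification of the exit visits, and Sections 4, 7.5.1, 7.5.3 and 7.8.6 point the same way. A site could read 7.5.2 as ending scheduled visits only after the exit procedures. This stands in part: most of the protocol sends sites to the right action, and data are lost only where a site takes 7.5.2 at its word. But 7.5.2 contains no such qualification, and nothing gives footnote x precedence.

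Second, asking to leave the study, as opposed to stopping the drug, can itself withdraw consent to follow-up. This stands. A reader might infer that 7.5.2 is wrong for everyone who asks to leave; the documents do not support that. The fault is that the section does not draw the distinction. Inability to comply is the firmer case.

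Third, Sections 7.5.1 and 7.8.6 describe a request and an attempt, so neither guarantees attendance. This also stands, and it is why the loss is given as up to two visits.

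Fourth, safeguards remain. Section 9.3.9 keeps investigators responsible for adverse events that caused a participant to leave, Section 9.3.9.3 continues follow-up of known events, Section 9.3.9.1 requires reporting of later-learned related serious events, and Section 9.3.9.5 collects pregnancies to 28 days after the last dose. All of this stands. None of it actively looks for new off-drug events.

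A reader might also infer that 7.5.2 cancels the monthly HBV DNA tests that exclusion criterion 16 requires for six months after the last dose. The documents do not support counting these as lost. The monitoring outlasts the four-week End of Study visit for everyone and is not a row in the ET or End of Study columns, so it is a separate commitment.

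**Conclusion.** Section 7.5.2 is wrong as written: it states a rule that conflicts with the rest of the protocol for dosed participants who cannot or will not comply and, because it does not ask about consent to follow-up, for some who ask to leave. Severity is low.

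The size is up to two scheduled safety visits and up to 28 days of active off-drug adverse event collection per participant whose site follows 7.5.2. The effect on the analysis is one-directional, toward lower treatment-emergent counts, in safety summaries that SAP Section 3.6 describes as essentially descriptive.

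This rests on two conditions: that the site follows 7.5.2 rather than footnote x, and that the participant would have attended if asked. A reader might want a number of participants affected. The documents give no withdrawal rate and no split by reason, so any such number would be an assumption and none is offered.

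**What to change.** Reword Section 7.5.2 in three respects:

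- Limit the rule against further visits to participants who withdraw consent for follow-up.
- State that all other dosed participants who stop, whether for non-compliance or at their own request, discontinue study drug and are asked to complete the existing ET visit and the four-week End of Study visit. Where they cannot attend, collect adverse events remotely; Appendix 9 already describes such a contact and can serve as the model.
- Cross-refer to Sections 4, 7.5.1 and 7.8.6 and to Table 1 footnote x, so that all give one instruction.

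The cost is a few sentences in the next protocol amendment, which under Section 12.1 needs ethics approval in any case. No visit or procedure is added, since both exit visits already stand in Tables 1 to 3, and the SAP needs no change.
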